2.6 Determination of sample size

In the event that 2 data analyses are conducted to accommodate an extended enrollment period in China, the initial data cut and analysis will be performed after all randomized non-Chinese subjects (approximately 400) have completed or terminated the study. The safety and efficacy analyses from this first data cut will serve as the basis for the European, North American, and Japanese submissions for marketing authorization. The power for this analysis is greater than 90%, at the 2-sided 5% significance level. Because of uncertainty regarding the time point when China will join the global program and the duration of recruitment in China, a second efficacy and safety analysis for all randomized subjects will also be performed: the power in this case remains greater than 90%, at the 2-sided 5% significance level. The safety and efficacy analyses from the second data cut will serve as the basis for submission for marketing authorization only for China.

The sample size was calculated based on achieving 90% power to observe a statistically significant result for either the 400mg bid and 200mg bid or 200mg bid and 100mg bid doses when compared to PBO for both the primary variable for FDA/PMDA/CFDA, change from Baseline of the log transformed ($\ln x+1$) 28-day adjusted seizure frequency, and the primary variable for EMA, the 75% responder rate. The log reduction from Baseline in seizure frequency was assumed to be 0.195 for PBO and 0.670, 0.754, and 0.780 for 100mg bid, 200mg bid, and 400mg bid doses of PSL, respectively. A common SD of 0.985 was assumed. For the 75% responder rate endpoint, assumptions were a 0.121 responder rate for PBO and corresponding responder rates of 0.301, 0.332, and 0.342 for the 100mg bid, 200mg bid, and 400mg bid doses of PSL, respectively. These estimates are based on prior experience in epilepsy together with the EP0069 study results. A significance level of 0.05 was chosen, and a 2-sided test assumed. With power of greater than 90%, a 2-sided Type-1 error of 5%, and all dose groups of the same size, 100 subjects are required per arm, giving a total of 400 subjects.

3 DATA ANALYSIS CONSIDERATIONS

3.1 General presentation of summaries and analyses

Statistical analysis and generation of tables, figures, subject data listings, and statistical output will be performed using SAS Version 9.3 or higher. All tables and listings will use Courier New font size 9.

Descriptive statistics will be displayed to provide an overview of the study results. For categorical variables, the number and percentage of subjects in each category will be presented. Unless otherwise noted, all percentages will be displayed to 1 decimal place. No percentage will be displayed for zero counts, and no decimal will be presented when the percentage is 100%. For continuous variables, descriptive statistics will include number of subjects with available measurements (n), mean, SD, median, minimum, and maximum.

Decimal places for descriptive statistics will always apply the following rules:

- “n” will be an integer

- Mean, SD, and median will use one additional decimal place compared to the original data
- Minimum and maximum will have the same number of decimal places as the original value.

Unless otherwise specified, statistical tests of efficacy variables will be presented as two-sided p values rounded to three decimal places. P-values less than 0.001 will be presented as “<0.001” and p-values greater than 0.999 will be presented as “>0.999.” Statistical comparisons will be two-sided and will be performed at the 0.05 level of significance.

A complete set of data listings containing all documented data as well as calculated data (e.g., change from Baseline), as applicable, will be generated.

Treatment groups will be displayed as: Placebo, PSL 100mg bid, PSL 200mg bid, and PSL 400mg bid.

Log-transformation is based on natural logarithm. For analyses on log-transformed values, model estimates will be back-transformed to anti-log space for table presentation. See Section 8.1.1 for details.

Data collected at scheduled visits will be included in the by-visit summary. Data collected at unscheduled visits will not be included in the by-visit summary, but will be considered when determining the Last Visit, minimum, and maximum post-Baseline values during the Treatment Period. Data collected on Visit 8 will be summarized separately for subjects in the Conversion Period versus the Taper and Safety FU Period.

In general, all CRF data will be presented in the subject listings.

3.2 General study level definitions

3.2.1 Initial processing of diary data for seizure frequency

Subjects are instructed to record in their diary all types of seizures that occur, after each seizure or at least once a day. The investigator will assess and confirm the seizures according to the ILAE codes (ILAE Classification of Epileptic Seizures, 1981) and record the seizure types and frequency in the eCRF/diary. With regard to cluster seizures, investigators are to report the number of cluster episodes rather than reporting the estimated number of individual seizures.

3.2.2 Analysis time points

3.2.2.1 Relative day

Study day for each subject is calculated relative to the date of the first administration of study drug. The date format in the study is dd-MMM-yyyy. Relative day is calculated as the current date in the study minus the date of first dose of study drug for days prior to the first dose of study drug, and the current date minus the date of first dose of study drug plus 1 for days on or after the day of first dose of study drug and prior to or on the day of last study drug dose (e.g., the day of first dose will be Day 1 and the day prior to first dose will be Day -1). For days after the last dose

of study drug, relative day will be calculated as the current date minus the date of last dose of study drug and including a “+” to denote posttreatment days (e.g., the day after the last dose will be Day +1).

Similarly, relative days for an event or measurement occurring before a reference date (generally the date of the first dose of study drug) are calculated as follows:

- Relative Day = (Event Date-Reference Date)

Relative days for an event or measurement occurring on or after the reference date to the last day of dose administration are calculated as follows:

- Relative Day = (Event Date-Reference Date) + 1

For events or measurements occurring after the date of last dose of study drug (as defined above), the relative day will be calculated with the date of last dose administration as reference. Relative day in this case will be prefixed with ‘+’ in the data listings and will be calculated as follows:

- Relative Day = + (Event Date-Reference Date)

3.2.2.2 End of the 16-week treatment period

The end of the 16-week overall treatment period will be either the date of Visit 7 for subjects completing the Treatment Period, or the date of the early discontinuation visit (EDV), for subjects who discontinued during the Treatment Period. If a subject does not have a Visit 7/EDV, then the date of the last contact will define the end date of the Treatment Period.

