#### Safety Follow-up Period (1 month)

Safety follow up for all subjects not entering the OLE will consist of 1 required visit, 30 days after the last IMP intake (Week 23 or sooner in case of early discontinuation), including an echocardiogram. An additional follow-up echocardiogram will be performed at 6 months ( $\pm 1$  month) after the last IMP intake only for subjects exposed to IMP for more than 3 weeks.

*For subjects continuing to the OLE study:*

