3.2.3 Analysis periods

The start and end dates of each analysis period (following the study design) are used for the classification of efficacy and safety data. The exact start and end of each of these periods is described for calculation purposes in [Table 3-1: Start and end of EP0092 analysis periods](#). Note that measurements obtained from diaries returned on the start date of the Titration and Stabilization Period would be included in the Baseline Period calculations. Refer to [section 3.3.1](#). Similarly, measurements from diaries returned on the start date of a subsequent period would be included in calculations for the previous period.

Table 3–1: Start and end of EP0092 analysis periods

Analysis Period			Details
Description	Start	End	
Baseline (Week -4)	Date of informed consent at Visit 1	Date of the day before the date of Visit 2.	This is an approximate 28-day period for calculation of Baseline seizure frequencies. Study drug is dispensed, and first dose is generally taken the day of the Baseline Visit (Visit 2, Day 1). Note the pre-dose assessments will also be included in the Baseline Period.
Titration and Stabilization*	The date of the Baseline Visit, (Visit 2, Day 1).	The date of the day before Visit 4 or the end of the treatment period if the subject has discontinued prior to Visit 4.	For evaluation purposes, if results are presented by analysis period, the Titration and the Stabilization interval will be considered together (approximately 4 weeks in total). Titration is a period of dose increases to reach the protocol specified dose. Stabilization is an approximate week-long interval to stabilize at the target dose level. During stabilization the dose may be adjusted once (i.e. to a fallback dose).
Maintenance*	The date of Visit 4.	The date of Visit 7 or the end of the treatment period if the subject has discontinued prior to Visit 7.	This is a 12-week period where the subject remains on the randomized target dose (or fallback dose, if applicable).
16-week Treatment Period*	The date of the Baseline visit (Visit 2)	The date of Visit 7 or the end of the treatment period if the subject has discontinued prior to Visit 7.	Titration and Stabilization Period and Maintenance Period combined.
Conversion	The date of the day after Visit 7	The date of Visit 8.	This is a 3-week period of dose conversion to enable the subjects to enroll into the OLE study EP0093.

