Taper and Safety Follow-up	The date of the day after Visit 7/EDV or the date of day after Visit 8 if the subject tapered after conversion	The date of final contact.	Subjects who withdraw from the study or decide not to participate in the OLE study will be tapered off the IMP during a 3-week period followed by a 1-week drug-free period. A SFU visit will be performed 30 days after the last IMP intake.

OLE=open-label extension; SFU=Safety Follow Up

* Only seizure data prior to and on the date of last dose of study medication will be included in the analysis.

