10.1 Extent of exposure

Extent of exposure will be based on the SS. The date of first dose is reported on First Administration of Study Medication CRF. The date of last dose is reported on the Study Termination CRF. If the date of last dose is missing due to lost to follow-up, the date of the last scheduled or unscheduled visit will be used.

The duration of study drug exposure for the Treatment Period will be calculated as the date of the last dose of study drug during the 16-week Treatment Period minus the date of first dose of

study drug plus 1 day. Date of the last dose of study drug during the 16-week Treatment Period is defined as the overall study last dose date or the end date of the 16-week Treatment Period, whichever is earlier.

Exposure (in days) will be summarized as a continuous variable for the 16-week treatment period. The number and percentage of subjects with the following categories of durations of exposure for the Treatment Period will also be summarized: >0 weeks, >=4 weeks, >=8 weeks, >=12 weeks, >=16 weeks.

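### For a subject with no Visit 7 or EDV, the SAP runs the Treatment Period to the last contact and gives Taper/Safety Follow-up no start date, so off-drug safety data fall in the Treatment Period tables

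*SAP*

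**What the plan says.** SAP Section 3.2.2.2 ends the Treatment Period at Visit 7 for completers and at the EDV for early discontinuers. It then adds a fallback for a subject with neither visit: "then the date of the last contact will define the end date of the Treatment Period". The fallback has no limit at the last dose.

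SAP Section 3.2.3 states that the period dates "are used for the classification of efficacy and safety data". In Table 3-1, Maintenance and the 16-week Treatment Period both end on "The date of Visit 7 or the end of the treatment period if the subject has discontinued prior to Visit 7". Titration and Stabilization uses the same fallback for a subject who stops before Visit 4.

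Taper and Safety Follow-up starts on "The date of the day after Visit 7/EDV or the date of day after Visit 8 if the subject tapered after conversion" and ends on "The date of final contact". No start is given for a subject who has no Visit 7/EDV and did not go through conversion.

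SAP Section 10.1 handles exposure differently. The last dose date within the Treatment Period "is defined as the overall study last dose date or the end date of the 16-week Treatment Period, whichever is earlier".

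Contact after the last dose is planned. Protocol Section 5.1 states: "Safety follow up for all subjects not entering the OLE will consist of 1 required visit, 30 days after the last IMP intake".

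**The concern.** The SAP tabulates treatment-emergent AEs (TEAEs) separately for the Treatment Period and for Taper and SFU. That separation lets a reader distinguish events on drug from events after stopping. For a subject with no Visit 7/EDV who is contacted later, it fails in two ways: off-drug time is labelled Treatment Period, and the period meant to hold it does not exist.

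These Treatment Period outputs can be affected:

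- TEAE tables, including those by relationship and by intensity, and the duration summaries for five named events, one of which is headache (SAP 10.2).
- Laboratory abnormality and liver-injury criteria counts (10.3, 10.3.1), and vital-sign and ECG abnormality counts (10.4.1, 10.4.2).
- The Last Visit, minimum and maximum rows. Last Visit is the last non-missing assessment in the Treatment Period (3.2.5), so an SFU result could be shown as the final on-treatment value.
- The disposition summary of subjects entering each period (5.1), where a subject who attended follow-up has no Taper/SFU period to enter.

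Protocol Section 2.3.1 describes new headache and sleep disturbance after stopping the drug. It calls them mild, transient, unrelated to dose and not of clinical concern. Even so, they are the events that the Taper/SFU table should show.

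**Working it through.** The plan gives no figure to reproduce. The check applies its own date rules to example subjects.

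**Inputs**

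- L: study day of last intake, with first dose on Day 1 at Visit 2. The documents give no values, so 7, 28, 56 and 84 are assumed.
- g: days from last intake to last contact. It is 0 if the subject is lost at the last dose, and 30 at an SFU contact. The ±7-day window (Protocol Table 5-1 and Section 8.4) gives 23 to 37.
- C = L + g: study day of last contact.

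**Formulas under the SAP as written**

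- Treatment Period for safety data: C days (Section 3.2.2.2).
- Exposure: min(L, C) = L days (Section 10.1).
- Off-drug days labelled Treatment Period: C − L = g. Their share is g / C.
- Taper/SFU: no defined start, so no days.

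| L | C at g = 30 | Share, g = 30 | Share, g = 23 | Share, g = 37 |
|---|---|---|---|---|
| 7 | 37 | 30/37 = 81% | 23/30 = 77% | 37/44 = 84% |
| 28 | 58 | 30/58 = 52% | 23/51 = 45% | 37/65 = 57% |
| 56 | 86 | 30/86 = 35% | 23/79 = 29% | 37/93 = 40% |
| 84 | 114 | 30/114 = 26% | 23/107 = 21% | 37/121 = 31% |

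At g = 0 the share is 0% for every L. In the last row the labelled period reaches Day 114, past the scheduled Visit 7 on Day 112.

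For L = 28 and g = 30, safety data have a 58-day Treatment Period against 28 days of exposure. If the period is cut at last dose, the Treatment Period is 28 days and Taper/SFU is 58 − 28 = 30 days.

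**Which data have a last-dose limit**

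| Data | Limit | Where in the SAP |
|---|---|---|
| Seizure data, hence both primary endpoints | Last dose | Table 3-1 footnote; Section 8 |
| Exposure | Last dose or period end, whichever is earlier | 10.1 |
| Treatment and diary compliance | Last dose | 7.1, 7.2 |
| CIWA-B withdrawal scale | Summarised by scheduled visit | 10.4.4.5 |
| TEAEs by period | None | 10.2 |
| Laboratory, vital-sign and ECG Treatment Period summaries | None | 10.3, 10.4.1, 10.4.2 |

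The SAP cuts seizure, exposure and compliance data at the last dose but sets no such cut for the safety data in the last two rows.

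**The case against.** The strongest case on the other side is that the trigger is narrow and nothing is lost.

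- **Few subjects.** Early discontinuers are required to return for an EDV. The error needs someone who misses that visit and is still contacted well after the last dose. A subject lost at the last dose adds no off-drug days. Where loss to follow-up leaves the last dose date missing, Section 10.1 sets it to the last visit, which shrinks the gap further. This stands and limits the size.
- **No events disappear.** The primary safety variables cover the entire study, and Section 10.2 summarises TEAEs at any time during it. Listings mark post-dose days with a plus sign (3.2.2.1), so affected events can be found. This stands for the totals, but it does not make the period tables right.
- **The intent is visible.** The Details column of Table 3-1 places the SFU visit in the Taper/SFU period. That supports the repair, but the written start rule still gives this subject no date.

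A reader might also infer more than the documents support:

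- **That efficacy is biased.** It is not, because seizure data stop at the last dose.
- **That about 180 off-drug days could be labelled Treatment Period, through the 6-month echocardiogram.** AEs are collected to the end of SFU, about 30 days after last intake, and study termination for these subjects is at Visit 9. Only SAE reporting runs to 6 months, and nothing makes the echocardiogram the defining last contact.
- **That the error grows with dropout in an arm.** Dropouts with an EDV do not trigger it. Only a difference between arms in missed EDVs followed by later contact would matter, and the documents suggest none.
- **That withdrawal events never reach a follow-up table.** A subject who tapers after Visit 8 has a defined start, although the period would then overlap the Treatment Period. Serious TEAEs and TEAEs leading to discontinuation have no Taper/SFU table for anyone, so there the effect is only added Treatment Period counts.

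The ECG effect is uncertain. The schedule's footnote makes the SFU ECG conditional on an abnormal end-of-treatment or EDV tracing, while Protocol Section 8.4 lists it without condition.

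**Conclusion.** Wrong as written, minor, and confined to the safety tables by period. The rule misplaces off-drug safety data for any subject with no Visit 7/EDV who is contacted after the last dose. An SFU contact would put about 30 days (23 to 37) in the wrong period.

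The conclusion assumes that last contact in Section 3.2.2.2 and final contact in Table 3-1 are the same date, which the SAP does not say. Taper/SFU lacks a start either way. The percentages in the working rest on assumed last-dose days. The documents give no count or rate of missing Visit 7/EDV, so no effect on any table's percentages can be estimated.

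**What to change.** In SAP Section 3.2.2.2, replace the fallback with: for a subject without Visit 7 or an EDV, the Treatment Period ends on the earlier of the date of last contact and the date of last IMP intake; where taper IMP was taken, use the day before the first taper intake in place of the last intake.

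In Table 3-1, add to the Taper and Safety Follow-up start: for these subjects, the day after that date, unless the subject entered Conversion.

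The cost is two sentences and one derived date. Section 5.1 already takes the last-administration and final-contact dates from the Study Termination CRF, so no new data are needed.

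There are two downsides. A few post-dose events move from the Treatment Period tables to the Taper/SFU table. Subjects whose EDV falls after their last dose still follow the EDV-date rule, so some off-drug days remain in their Treatment Period; the SAP should state that this is accepted.

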3.2.3 Analysis periods

The start and end dates of each analysis period (following the study design) are used for the classification of efficacy and safety data. The exact start and end of each of these periods is described for calculation purposes in [Table 3-1: Start and end of EP0092 analysis periods](#). Note that measurements obtained from diaries returned on the start date of the Titration and Stabilization Period would be included in the Baseline Period calculations. Refer to [section 3.3.1](#). Similarly, measurements from diaries returned on the start date of a subsequent period would be included in calculations for the previous period.

Table 3–1: Start and end of EP0092 analysis periods

Analysis Period			Details
Description	Start	End	
Baseline (Week -4)	Date of informed consent at Visit 1	Date of the day before the date of Visit 2.	This is an approximate 28-day period for calculation of Baseline seizure frequencies. Study drug is dispensed, and first dose is generally taken the day of the Baseline Visit (Visit 2, Day 1). Note the pre-dose assessments will also be included in the Baseline Period.
Titration and Stabilization*	The date of the Baseline Visit, (Visit 2, Day 1).	The date of the day before Visit 4 or the end of the treatment period if the subject has discontinued prior to Visit 4.	For evaluation purposes, if results are presented by analysis period, the Titration and the Stabilization interval will be considered together (approximately 4 weeks in total). Titration is a period of dose increases to reach the protocol specified dose. Stabilization is an approximate week-long interval to stabilize at the target dose level. During stabilization the dose may be adjusted once (i.e. to a fallback dose).
Maintenance*	The date of Visit 4.	The date of Visit 7 or the end of the treatment period if the subject has discontinued prior to Visit 7.	This is a 12-week period where the subject remains on the randomized target dose (or fallback dose, if applicable).
16-week Treatment Period*	The date of the Baseline visit (Visit 2)	The date of Visit 7 or the end of the treatment period if the subject has discontinued prior to Visit 7.	Titration and Stabilization Period and Maintenance Period combined.
Conversion	The date of the day after Visit 7	The date of Visit 8.	This is a 3-week period of dose conversion to enable the subjects to enroll into the OLE study EP0093.
Taper and Safety Follow-up	The date of the day after Visit 7/EDV or the date of day after Visit 8 if the subject tapered after conversion	The date of final contact.	Subjects who withdraw from the study or decide not to participate in the OLE study will be tapered off the IMP during a 3-week period followed by a 1-week drug-free period. A SFU visit will be performed 30 days after the last IMP intake.

OLE=open-label extension; SFU=Safety Follow Up

* Only seizure data prior to and on the date of last dose of study medication will be included in the analysis.

3.2.4 Mapping of assessments performed at early discontinuation

Unlike other scheduled visits, an early discontinuation visit (EDV) doesn't have a predetermined visit window and can occur at any days during the study. If an EDV occurs at the day of a scheduled visit, assessments (in-clinic safety assessments such as vital signs, ECGs, and blood collection for clinical laboratory assessments) should correspond to that scheduled visit.

Assessments at an EDV that occurs on a day between two scheduled visits will be assigned to the next scheduled visit. All other assessments (such as questionnaire and PK samples) collected on an EDV will not be mapped.

In the by-visit summary tables, only nominal (scheduled) visits where the assessment is scheduled will be included. For example, if a subject had an EDV after Visit 4 and before Visit 5, the applicable assessments will be mapped to Visit 5 (ie, the next scheduled visit). Vital signs and ECGs collected at the EDV will be summarized under Visit 5 in the by-visit summary tables. However, Visit 5 will not be included in the by-visit summary tables for the clinical laboratory assessments as lab assessments are not scheduled on Visit 5. Unscheduled visits will not be mapped to scheduled visits. In the subject listing, data will be presented under the actual visits, including EDV and unscheduled visits.

Seizure data collected by diary are associated with periods defined within the study and as such need no mapping to visits. If a subject withdraws between visits an effort is made to recover all diary records for use in calculation of seizure frequencies.

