#### Taper Period (4 weeks)

The 4-week Taper Period will be required for subjects who choose not to enroll in the OLE study or who discontinue the study. Subjects entering the 4-week Taper Period should be gradually

tapered off the IMP over a 3-week period (Table 7-3) followed by a 1-week drug-free period. A faster or slower taper schedule than the suggested 3 weeks may be implemented, if medically necessary, as per the Investigator's medical judgment. Subjects will start their taper at the EDV/End of Treatment Visit (Visit 7) and will return 1 week after last intake of IMP for the End of Taper Visit (Visit 8). Changes to concomitant AED(s) are not allowed during the taper of PSL unless they are medically necessary as per the Investigator's medical judgment to treat rebound seizures.

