**Table 5-1: Schedule of assessments**

Visit	BL Period (4 weeks)	Treatment Period (16 weeks)										Taper/Conversion Period (3 to 4 weeks) a	SFU Period (30 days after IMP intake)	Unsch Visit b	
		Titration Period (3 weeks)			Stab Period (1 week)	Maintenance Period (12 weeks)									
		V2 BL	TC	V3	TC	V4	V5	V6	V7 (EDV/EOT)	TC	V8 (Conversion)				V8 (Taper)
Week Number	Wk -4	D 1	Wk 1	Wk 2	Wk 3	Wk 4	Wk 8	Wk 12	Wk 16		Wk 19	Wk 20	Wk 23		
Health-related outcomes and HRU	X	X		X		X	X	X	X			X		X	
IMP dispensing (IRT)		X		X		X	X	X	X						
IMP accountability and return f				X		X	X	X	X			X			
Study termination g												X		X	

AED=antiepileptic drug; BL=Baseline; CIWA-B=Clinical Institute Withdrawal Assessment-Benzodiazepines; C-SSRS=Columbia-Suicide Severity Rating Scale; D=day; DBP=diastolic blood pressure; ECG=electrocardiogram; EDV=Early discontinuation Visit; EEG=electroencephalogram; EOT=End of Treatment; HADS=Hospital Anxiety and Depression Scale; HRU=healthcare resource utilization; IMP=investigational medicinal product; IRT=interactive response technology; MRI=magnetic resonance imaging; OLE=open-label extension; PK=pharmacokinetic; PSL=padsevonil; QOLIE-31-P=Quality of Life Inventory in Epilepsy-31-P; SBP=systolic blood pressure; SFU=Safety Follow-Up; SSG=Seizure Severity Global Item; Stab=Stabilization Period; TC=telephone call; TSQM=Treatment Satisfaction Questionnaire for Medication; Unsch=unscheduled; V=visit; Wk=Week

a Taper Period, for subjects who choose not to enter OLE study EP0093, will last for 3 weeks plus 1 week of drug-free period. Conversion Period, for subjects who choose to enter OLE study EP0093, will last for 3 weeks.

b At any time, the subject may have an additional study visit if the Investigator or the subject and/or legal representative deem it necessary. Appropriate assessments will be conducted in relation to the reason for the visit.

c Epileptic seizures must have been documented using video-EEG recording in the past (description or report must be available). The Investigator must consult with the UCB Study Physician or representative for confirmation of eligibility as per instructions in the Study Manual.

d Questionnaires to be completed by all subjects prior to any other study procedures at the visit. The CIWA-B will only be completed by subjects tapering.

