### **11.7.8 Withdrawal monitoring**

Any symptoms of withdrawal reactions will be monitored using the CIWA-B questionnaire at the scheduled time points presented in [Table 5-1](#). The CIWA-B questionnaire contains 22 questions which are selected to distinguish withdrawal symptoms from other symptoms (Busto et al, 1989).

Subjects should be monitored during the Taper Period for withdrawal symptoms, including withdrawal-related AEs or seizures as well as the severity of the CIWA-B withdrawal scores. Withdrawal symptoms may require medical treatment for management of severe withdrawal symptoms.

Further details about this questionnaire will be covered in the Study Manual.

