2.3.2 Other safety variables

Other safety variables are as follows:

- Incidence of TEAEs reported by the subject and/or caregiver or observed by the Investigator during the following periods: 16-week Treatment Period, 12-week Maintenance Period, 4-week Titration/Stabilization Period, and 3-week Taper Period
- Number of and reason for subjects requiring premature tapering due to TEAEs
- Number of and reason for subjects requiring a dose reduction during the Stabilization Period due to TEAEs
- Incidence of treatment-emergent SAEs during the following periods: 16-week Treatment Period, 12-week Maintenance Period, 4-week Titration/Stabilization Period
- Changes in clinical laboratory test parameters (including hematology, blood chemistry, and urinalysis)
- Changes in vital sign parameters (including pulse rate, systolic BP, diastolic BP, and respiratory rate)
- Changes in 12-lead ECG parameters

- Physical examination (including body weight) and neurological examination findings
- Changes in Psychiatric and Mental Status
- Occurrence of valvular abnormalities or pericardial effusion changes or other significant abnormalities as identified by 2-dimensional Doppler echocardiogram at each assessment by central reader
- Changes in withdrawal symptoms using Clinical Institute Withdrawal Assessment-Benzodiazepines (CIWA-B) from the End of Treatment Visit (Visit 7) to end of the Taper Period (Visit 8) and end of the SFU Period (Visit 9 [30 days after the last IMP intake]).

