10.4.4.5 Clinical Institute Withdrawal Assessment-Benzodiazepines (CIWA-B)

Subjects not entering the open label extension study (OLE) are tapered off study medication after completing the Maintenance Period (or if discontinued from the study). As part of monitoring of subjects for withdrawal symptoms during the Taper Period, the CIWA-B evaluation is performed at the end of the Maintenance Period (Visit7), at the end of the Taper Period (Visit 8), and at the Safety follow-up visit (Visit 9). The CIWA-B questionnaire contains 22 questions, which are utilized to determine the type and the severity of withdrawal symptoms, ranging from mild, moderate, severe and very severe withdrawal symptoms (Busto et al, 1989). Subscores of each of the first 20 questions (scores from 0-4) are summed up to a total score:

Total score	Interpretation
-------------	----------------

1-20	Mild withdrawal
21-40	Moderate withdrawal
41-60	Severe withdrawal
61-80	Very severe withdrawal

In case of a missing sub score the total score is set to missing. The remaining two items of the 22 ask for sleeping duration and time to fall asleep. A by-subject listing will be provided, presenting the response values to all assessment parameters as well as the CIWA-B scores. In addition, a descriptive summary table will be prepared for total CIWA-B scores at scheduled visits.

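### Followed literally, the SAP leaves early discontinuers' start-of-taper CIWA-B score out of the Visit 7 row but keeps them at Visits 8 and 9, and the declared change from Visit 7 is never tabulated

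*SAP*

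**What the plan says.** CIWA-B is collected at Visit 7 or the EDV, at Visit 8 and at Visit 9 (protocol Table 5-1; sections 8.2.3.3, 8.3.2 and 8.4). Footnote d of Table 5-1 limits who completes it: "The CIWA-B will only be completed by subjects tapering". Two groups taper: subjects who discontinue early and completers who decline the extension study. Both begin at the same nominal point. Protocol 5.1 says: "Subjects will start their taper at the EDV/End of Treatment Visit (Visit 7").

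The declared variable is a change. SAP 2.3.2 lists "Changes in withdrawal symptoms using Clinical Institute Withdrawal Assessment-Benzodiazepines (CIWA-B) from the End of Treatment Visit (Visit 7") to Visit 8 and to Visit 9. Protocol 4.2.2 says the same.

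SAP 3.2.4 treats the EDV as separate from the scheduled visits. In-clinic safety assessments taken there go to the coinciding or next scheduled visit. For the rest: "All other assessments (such as questionnaire and PK samples) collected on an EDV will not be mapped". It adds: "In the by-visit summary tables, only nominal (scheduled) visits where the assessment is scheduled will be included". Protocol 11.7.8 leaves no doubt about which kind of assessment this is: "Any symptoms of withdrawal reactions will be monitored using the CIWA-B questionnaire at the scheduled time points".

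For the output, SAP 10.4.4.5 plans a by-subject listing, and in addition "a descriptive summary table will be prepared for total CIWA-B scores at scheduled visits". It mentions no change score.

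**The concern.** A table meant to show what happens when the drug is withdrawn needs the same subjects before and after taper. Under 3.2.4, an early discontinuer's pre-taper score has no scheduled visit to sit under, while the Visit 8 and Visit 9 scores do. The Visit 7 row would then hold only completers who declined the extension, and the later rows would hold those completers plus the early discontinuers.

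The question matters to this programme. Protocol 2.3.1 describes new events after stopping in Phase 1 as indicating a potential withdrawal syndrome, and protocol 2.4 lists substance abuse and dependence among the potential risks. CIWA-B is the withdrawal scale the protocol prescribes. If early discontinuers score differently from completers, for instance because they stopped for CNS events, the Visit 7 to Visit 8 comparison mixes that difference with any effect of taper.

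**Working it through.** The documents state no figure for this point, so there is none to reproduce. The check follows the rules for each type of subject and then asks how many subjects are affected.

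**1. Tracing the rules**

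- *Completer who declines the extension.* Scores fall at Visits 7, 8 and 9, all scheduled, so this subject is in all three rows.
- *Early discontinuer.* Scores fall at the EDV, Visit 8 and Visit 9. The EDV score is a questionnaire and is not mapped (3.2.4), so this subject is absent from the Visit 7 row and present in the other two.
- *If CIWA-B were instead treated as an in-clinic safety assessment.* It would go to the coinciding or next scheduled visit. Unless that is Visit 7, CIWA-B is not scheduled there, and 3.2.4 drops it from the table anyway.
- *Other reference value.* SAP 3.3.2 defines Baseline as the last value before first dose. CIWA-B is first collected at Visit 7/EDV, so Baseline cannot supply one.
- *Recorded change of plan.* SAP 3.9 has no entry dropping the change variable.

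**2. What the mismatch does to the table**

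Let p be the share of tapering subjects who discontinued early, and let mc and md be the start-of-taper mean scores of completers and discontinuers. Assume all attend Visit 8 and nobody's score changes.

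- Visit 7 row mean = mc
- Visit 8 row mean = (1 − p)·mc + p·md
- Apparent change = p·(md − mc)

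The table would show a shift although no one changed. If discontinuers truly rise by Δ, the apparent change is p·(md − mc) + p·Δ, and the table cannot separate the two parts.

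**3. How large p could be**

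Let d be the proportion discontinuing early and r the extension uptake among completers. Completers who decline also taper, so

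p = d / [d + (1 − d)(1 − r)], which exceeds 50% only when d > (1 − r)/(2 − r).

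The documents give neither d nor r for EP0092. The ranges are assumptions: d 5–30%, r 50–95%. The one uptake figure available is from the earlier EP0069 study (protocol 2.3.1), 42/55 = 76.4%. It is a weak proxy, because its denominator is all subjects rather than completers and the design was different.

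| r | p at d = 5% | p at d = 30% | d above which p > 50% |
|---|---|---|---|
| 50% | 9.5% | 46.2% | 33.3% |
| 76.4% | 18.2% | 64.5% | 19.1% |
| 90% | 34.5% | 81.1% | 9.1% |
| 95% | 51.3% | 89.6% | 4.8% |

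Example, r = 76.4% and d = 30%: 0.30 / (0.30 + 0.70 × 0.236) = 0.30 / 0.465 = 64.5%.

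**The case against.** The best reply is SAP 3.2.5. It puts a Last Visit row in by-visit summaries by default, holding the last non-missing assessment in the Treatment Period. SAP 3.2.2.2 ends that period on the EDV date for discontinuers. CIWA-B is scheduled once in the Treatment Period, so a Last Visit row would carry the start-of-taper score of every tapering subject. This stands as a possibility. But 10.4.4.5 confines its table to scheduled visits, whereas the laboratory, vital sign and ECG sections (10.3, 10.4.1, 10.4.2) name the Last Visit row explicitly. Two programmers could build different tables. Even if the row appears, it is an unpaired summary and gives no within-subject change.

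Second, protocol Table 5-1 labels the EDV and End of Treatment Visit together as Visit 7. That supports the fix, but it does not override the specific SAP rule that leaves EDV questionnaires unmapped. SAP 10.4.4.5 itself places Visit 7 at the end of the Maintenance Period.

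Third, listings show EDV data under the actual visit (3.2.4), and protocol 13.4.1 planned only listings for CIWA-B. Withdrawal-related events are also monitored during taper (protocol 7.2.2), and adverse events are tabulated for the Taper and Safety Follow-up Period (SAP 10.2). All of this stands and lowers the stakes. A reader might infer that a real rise in discontinuers could not be seen at all. That is not so, because it can be read subject by subject. What is missing is the arm-level paired summary.

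**Conclusion.** The point holds as a misalignment within the SAP. Applied literally, 3.2.4 and 10.4.4.5 give a Visit 7 row with a different population from the Visit 8 and 9 rows, and the change declared in SAP 2.3.2 and protocol 4.2.2 is not computed.

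Two stronger readings are tempting and should not be drawn. One is that most tapering subjects lack a Visit 7 score. The documents do not support this: completers who decline the extension do have one, and the affected share runs from about 10% to about 90% over the assumed ranges. Early termination of the study, the stated reason for SAP Amendment 1, might push the share up, but no count is given. The other is that discontinuers have no reference value anywhere in the table. The default Last Visit row may supply one.

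The severity is minor. The table is descriptive, with no test attached, and CIWA-B is an 'other' safety variable. The mismatch itself does not depend on the assumed rates; only its size does.

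**What to change.** 1. In SAP 3.2.4, add an exception: CIWA-B collected at the EDV is the start-of-taper value and is assigned to Visit 7.
2. In SAP 10.4.4.5, tabulate by treatment arm the within-subject change in total score from start of taper (Visit 7 or EDV) to Visit 8 and to Visit 9, in subjects with both values.

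A split by completer versus early discontinuer is optional, since the cells may be small.

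The cost is two sentences and one derived variable. The data are already collected, and no visit, form or procedure changes.
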